All other assessments will be double-entered and cleaned by research staff. Data files will be backed up weekly and stored on a password-protected computer. Staff will attempt to collect all missing assessments immediately post collection but no later than 1 month after study completion. Missed or incomplete assessments are anticipated. As a result, study staff will document the reason why assessments are missed in the study files. Missed assessments will not be documented or reported as protocol deviations for the purposes of this study.

Power Analysis and Sample Size Considerations. The primary purpose of this grant is to establish implementation factors and detect signal in constructs of interest (i.e., DD and WM) in preparation for a subsequent, fully-powered trial. Therefore, we present information

regarding required sample size for completeness, but highlight that this project is not intended to be powered to examine clinical effectiveness.

Missing Data. Because missing data can lead to biased estimates of effects and, consequently, incorrect interpretations of clinical trial outcomes, we will attempt to handle missingness in a number of ways, including employing participant retention procedures and collecting assessments even if the participant did not complete any or all of the computer training sessions. If data is missing, we will examine patterns of missingness to determine if specific missing data algorithms, such as multiple imputation or full information maximum likelihood approaches, would be appropriate for use with our data.

Next Steps. Findings for the current study will provide critical information for successfully completing future aims of this grant, including an RCT examining effectiveness of WM training in reducing adolescent DD and risk for SU, guided by the results of the current study. Results may also support utilizing the intervention adjunctively alongside more content-focused prevention efforts, supporting future comprehensive prevention trials to decrease SU. Developing cognitive training interventions targeting mechanisms of SU liability specific to adolescents exposed to early adversity has the potential to enhance both basic understanding of determinants of SU and intervention approaches in a vulnerable, traditionally underserved adolescent population.

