Research staff will bring any adolescents who report engaging in dangerous levels of risky behaviors, as indexed by severe and frequent episodes of substance use, to the attention of the investigator team during regular meetings. Based on information from study evaluations, Drs. [name] (PI) and [name] (Co-I located in Flint, proximal to the Flint Freedom Schools, and both licensed clinical psychologists) will determine the appropriate course of action. These actions will follow protocols and regulations stipulated by the community site (either YMCA/FFSC/ or DBG), HFHS IRB, NIH and the State of Michigan. In extreme circumstances, this may involve contacting authorities. Participants will be allowed to remain in the study, but their data will not be used and a replacement participant will be recruited. Incidents of suicidality or abuse not deemed to involve imminent danger will be considered an adverse event (AE) and incidents where imminent danger is evident will be considered a serious adverse event (SAE). Both AEs and SAEs will be promptly reported to appropriate institutional contacts.

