Train Your Brain: A Pilot Project to Improve Memory and Decision Making

NCT05879198

Final Approved Protocol

Document Date 8/16/2024

Data Analytic Plan

Primary Outcomes: Changes in delay discounting, time horizon, and executive functions.

Descriptive statistics will be used to characterize the sample and psychometric properties will be examined (reliability, etc.). Changes in quantitative measures (including delay discounting, time horizon, and executive functions) will be examined in a number of ways. First, we will examine each variable to evaluate mean, standard deviations, skew and kurtosis. We will examine the overall number of youth who demonstrated decreases in delay discounting (5-Trial Adjusting Measure of Delay Discounting). We will use *t*-tests and reliable change indices (RCI) to examine differences in mean levels of consideration of future consequences (Consideration of Future Consequences Scale) and measures of executive function (Tower of Hanoi, Letter Number Sequencing, Iowa Gambling Task). We will set statistical significance at $p < .05$.

Secondary Outcomes: Changes in risk behaviors.

Descriptive statistics will also be examined for all secondary outcomes. We will then evaluate changes in our measures of risky behaviors (the Youth Risk Behavior Survey and the Alcohol and Marijuana Expectancies measures) using *t*-tests and RCIs. We will set statistical significance at $p < .05$.

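### Protocol section 4 discards the data of, and replaces, enrolled youth flagged for severe, frequent substance use: a post-enrolment exclusion overlapping the secondary outcome, with scope and counting unstated

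*Protocol*

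**What the plan says.** Protocol section 4 concerns "any adolescents who report engaging in dangerous levels of risky behaviors, as indexed by severe and frequent episodes of substance use". Staff must bring each such case "to the attention of the investigator team during regular meetings". Two licensed psychologists on the team then decide what to do. Next comes "In extreme circumstances, this may involve contacting authorities", followed directly by the rule at issue: "Participants will be allowed to remain in the study, but their data will not be used and a replacement participant will be recruited".

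On the secondary outcomes the SAP says: "We will then evaluate changes in our measures of risky behaviors (the Youth Risk Behavior Survey and the Alcohol and Marijuana Expectancies measures". The methods named are t-tests and reliable change indices, at p < .05. It adds: "Descriptive statistics will also be examined for all secondary outcomes". It names no analysis set, exclusion or replacement rule.

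Other relevant places in the protocol:
- Section 2 excludes youth with a current substance use disorder diagnosis. It sets no limit on undiagnosed use.
- Section 3 collects substance use risk indicators at baseline, after consent. Everyone receives the active training.
- Section 3, Aim 1, measures feasibility from enrolment, attendance and retention.
- Section 3 and its enrolment table cap intervention youth at 50 and give no allowance for replacements.
- Section 3, Missing Data, opens with "Because missing data can lead to biased estimates of effects and, consequently, incorrect interpretations of clinical trial outcomes" and commits to "collecting assessments even if the participant did not complete any or all of the computer training sessions".

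**The concern.** The rule sits in a risk section but works as an analysis rule. A youth can be eligible, consented and trained, stay in the study, and still be removed from the results because of reported behaviour that overlaps a measured outcome. With no comparison arm, no second group is subject to the same selection.

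Two matters are open. **Scope:** because the rule follows the sentence on extreme circumstances, it may cover all flagged youth or only the extreme ones. **Counting:** nothing says whether a set-aside youth counts in the feasibility measures, or whether a replacement counts toward 50. Timing is less open, but no assessment point is named.

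At stake are the reported level of risk behaviour and the feasibility counts meant to guide the later randomised trial. The possible effect on mean change depends on timing.

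**Working it through.** The plan has no figure to reproduce: it gives no flag rate, SD, effect size or power. The sizes below illustrate the mechanism under stated assumptions.

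**Inputs from the documents.** Up to 50 youth, one arm, two assessments, significance at .05.

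**Assumed inputs.** No true change; normal scores standardised at each visit; baseline-to-post correlation r = 0.4-0.6; flag score correlated rho = 0.5 with the risk score at the same visit; the top fraction q flagged per visit, removed and replaced. The same cut-off c applies at both visits, and phi is the normal density.

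**1. Will anyone be flagged?** For a single visit, P(at least one of 50) = 1 - (1 - q)^50.
- q = 1%: 1 - 0.99^50 = 39%.
- q = 2%: 1 - 0.98^50 = 64%.

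Over two visits these rise to about 60-64% and 84-87%; the upper ends are close to independent flags, 1 - (1 - q)^100.

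**2. Flag at either visit (natural reading).** By simulation:
- Bias in mean change is within 0.002 SD of zero.
- At q = 4-10%, the one-sided false-improvement rate is 2.4-2.6% against a nominal 2.5%.
- At q = 1-2%, about 2-4% of youth are removed in total and the mean post-training risk level is 0.02-0.04 SD too low.
- At q = 4-10%, about 8-19% are removed and the level is 0.06-0.15 SD too low.

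Mean change is spared because the same selection lowers both visits equally.

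**3. Flag acted on at one visit only.** For post-intervention only, bias in SDs of change is

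-rho × (1 - r) × phi(c) / (1 - q) / sqrt(2(1 - r)).

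- rho = 0.5, r = 0.6, q = 4%: phi(c) = 0.0862, so -0.5 × 0.4 × 0.0862 / 0.96 / 0.894 = -0.020.
- rho = 0.5, r = 0.4, q = 10%: phi(c) = 0.1755, so -0.5 × 0.6 × 0.1755 / 0.90 / 1.095 = -0.053.
- q = 1-2%: 0.006-0.014 in size.

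The range is therefore about 0.01-0.05 SD, toward improvement. Baseline-only flagging gives the same size toward worsening.

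**4. Delay discounting.** One replaced youth can move the proportion who decreased by at most 1/50 = 2 percentage points, in an unknown direction.

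**5. Feasibility counts (illustration).** Suppose 40 of the first 50 are retained and 3 are flagged and replaced, so 53 enrol. These are extreme cases.

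| Case | Drop and replace | All enrolled |
|---|---|---|
| Flagged all retained, replacements all lost | 37/50 = 74% | 40/53 = 75% |
| Flagged all lost, replacements all retained | 43/50 = 86% | 43/53 = 81% |

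The cap is exceeded only if 50 are already enrolled when a replacement is sought.

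**The case against.** The strongest reply is that the rule covers any adolescent who reports such use, raised at recurring meetings with no visit limit. Read that way, the secondary t-tests on mean change are essentially unharmed. This stands, with two conditions: no true change, and the same cut-off at both visits. A reader might infer that the rule manufactures an apparent improvement. The documents do not support that. It would need flags acted on only after training, a restriction they do not state.

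A reader might also infer that section 4 contradicts the Missing Data paragraph. It does not. That paragraph concerns non-response and incomplete training, and collection can continue for youth who remain. Deliberately not using collected data sits uneasily with the aim of limiting bias, but it is a tension only.

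A third reply is that a prevention pilot in youth aged 12-14 may reasonably target those below severe use. That is a fair choice of population, but it belongs in the eligibility criteria before enrolment. Section 2 excludes only diagnosed disorder. What stands is that the level is understated relative to the enrolled sample, not relative to every population one might choose.

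Three further limits hold. The overlap with the Youth Risk Behavior Survey rests on shared wording, because its items and scoring are not listed, and the overlap with the expectancy measures is only indirect. Flag rates of 4-10% are pure assumption and may be high for such use at this age. Risk scores are likely skewed, which would change every size above, possibly upward.

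**Conclusion.** The concern holds in a limited form. As written, the plan removes and replaces enrolled youth on a construct that overlaps the secondary outcome, and the SAP does not restore them. On the natural reading, the lasting harms are an understated level of risk behaviour in the enrolled sample (0.02-0.04 SD at 1-2% flagged per visit, 0.06-0.15 SD at 4-10%) and ambiguous enrolment, attendance and retention counts. Bias in mean change is about zero on that reading with no true change. It reaches about 0.01-0.05 SD only if flags were acted on at a single visit, with the direction set by which visit.

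These sizes rest on normal scores, a flag-outcome correlation of 0.5 and assumed flag rates. If only extreme cases are covered, few or no youth may be affected. The counting ambiguity needs no such assumptions: one replaced youth is enough. Severity is minor to moderate, since the affected tests are secondary and the protocol disclaims power for effectiveness.

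**What to change.** In protocol section 4, remove the clause on not using the data and recruiting a replacement. In the SAP, state that all enrolled youth are kept in the primary, secondary and feasibility analyses whatever substance use they report. Report how many were flagged and at which assessment. Show results without them only as a labelled sensitivity analysis.

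If an IRB, legal or consent provision bars use of a youth's data, name it and say whether it covers all flagged youth or only extreme cases. Count that youth as enrolled with missing data, and state how any replacement counts toward the cap of 50. The safety-response steps are not at issue and stay unchanged.

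The cost is a short protocol amendment and two SAP lines, plus consent text if it repeats the clause (consent pages were not available to check). No extra data collection is needed if flagged youth who remain complete the planned assessments. The downside is that results may be slightly more variable or less favourable.

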5. ANTICIPATED BENEFITS

For youth participating the current study, the potential benefit of taking part in the clinical trial is the possible improvement in working memory, related executive function skills, and delay discounting, as well as subsequent improvement in health-related behaviors.

More broadly, for all youth participants, knowledge gained from this study will inform future substance use prevention efforts and will also help in refining dissemination procedures in low-resource communities. Thus, the primary benefit of the proposed research to the community is to inform future interventions that may reduce rates of adolescent substance use

and improve public health in this traditionally underserved area.

6. RENUMERATION/COMPENSATION

Youth Intervention Group: Compensation will be skewed such that rates of compensation will increase across the course of the intervention.

Child:

1. Baseline assessment = \$10
2. Post-intervention assessment = \$15
3. Key informant interview = \$20
4. Training session = 1 ticket (that can be turned in at regular intervals for prizes)
5. Improvement = 1 ticket/improved training module
6. Certificate of completion

Parent:

1. Baseline assessment = \$25
2. Post-intervention assessment = \$25
3. Key informant interview = \$25

Tickets issued for improved training modules are based upon the completion of computer training modules (AKA challenge tasks). Tickets can be turned in for prizes under \$10 in value. Examples of prizes include gift cards, games, school supplies, sporting posters and goods, one size clothing such as socks, fidget toys, stickers, candy, slime, and body care products like lotion. These incentive amounts were determined in collaboration with potential members of the Community Advisory Board and deemed commensurate with other interventions currently being conducted in Detroit and Flint and not coercive to potential participants.

Youth Focus Group: Compensation will be \$25/focus group provided by ClinCard following each focus group.

7. COSTS

Participation in the study is at no cost to the participants.

8. ALTERNATIVES

There are no other alternatives to participation.

9. CONSENT PROCESS AND DOCUMENTATION

Informed consent and assent will be obtained at the initial screening assessment. As part of this process, participants, and guardians will be given a detailed description of the purpose and procedures of the study, emphasizing our policy regarding privacy and confidentiality. Only individuals giving informed and voluntary consent/assent will be enrolled. All consent and assent documents will be reviewed and approved by the HFHS IRB prior to administration.

10. WITHDRAWAL OF SUBJECTS

Subjects may voluntarily withdraw from the study at any time with no penalty themselves or

their healthcare or insurance plans/benefits. In the event of safety concerns and/or due to the participant having exceptional difficulties with completing the questionnaires, the PI may decide to withdraw the participant from the study.

11. PRIVACY AND CONFIDENTIALITY

For this study, we will ensure the separation of de-identified participant data from protected health information (PHI) by storing data in separate locations. De-identified data will be stored using secure, password-protected software hosted on HFHS servers. All participant information will be referenced using participant identification numbers. De-identified participant responses to study measures will be collected and stored using REDCap, a software toolset and workflow methodology for electronic collection and management of data. Only the investigators/authorized staff will have access to the REDCap database. We will only keep a record of number of screenings completed and reasons for ineligibility.

We will need to collect names and demographic information for participants who complete consent. Once collected, data will be de-identified. The file containing the information that links participant names to their IDs will again be stored in password-protected files on the HIPAA compliant, secure REDCap file. Only investigators will have access to this file. The key linking identifiable information to the participant ID will be destroyed five years after publication of study results.

Once data are collected, all data will be de-identified, i.e. names will be removed and participants will be assigned ID numbers.

As part of the informed consent process, participants will be advised that they may decline to answer any questions. This will provide participants with the assurance of confidentiality around sensitive personal information relating to substance use and mental health. All personnel working on the project will be educated about the importance of respecting participants' rights to confidentiality. Investigators will all complete and maintain ethical and CITI training. All study personnel will be appropriately trained in the ethical conduct of human subjects' research.

Study files will be maintained until five years after the publication of study results in line with the guidelines of the American Psychological Association.

Due to Michigan law, we will disclose to the appropriate individuals and/or authorities any information that comes to our attention concerning child abuse or neglect, or thoughts of harm to self or others, or if a court of law ensures, a subpoena for the research records.

Important HIPAA Concerns

We will not be accessing electronic medical health records; we will, however, be collecting PHI on our patient locator form, demographics in our baseline and information to provide incentive through the ClinCard software.

We will collect and use:

- Name
- Address
- Telephone Number
- Email address
- Demographics

We may release this information to the following people:

- The Principal Investigator and his/her associates who work on, or oversee the research activities.
- Henry Ford Health Systems Institutional Review Boards (IRB)

No names, identifying pictures or other direct identifiers will be used in any public presentation or publication about this study unless you sign a separate consent allowing that use or sent outside of HFHS.

12. DATA AND SAFETY MONITORING PLAN

All research staff (including community liaisons) will complete relevant training in the protection of human subjects. Being proximally located to the data collection site, [name] will ensure that all participants meet inclusion/exclusion criteria and are appropriate for inclusion in the study. Data will be monitored on an ongoing basis and reviewed with the PIs at regular intervals. As data will be entered electronically, we do not foresee any concerns with inconsistent responses; however, should this problem arise, research staff will review all entries and determine a resolution.

All participant data and records will be maintained in a secure location accessible only to project staff. All data files will be stored under a randomly-assigned subject number and no identifiable information will be included in participant files. Consent forms and other documents with identifiable information will be kept in a separate, secured location. Any computers containing electronic data files will be password-protected and accessible only by study personnel. Only the PIs and the database administrator will have access to the data. Analyses will be conducted only after all data is collected, deidentified, and cleaned, thus limiting the possibility of deidentification. Any findings shared with community stakeholders will be done in aggregate and reflecting mean-level trends. We will also utilize the Certificate of Confidentiality provided by NIH to protect against requests to disclose sensitive research information, within the bounds of the law.

Adverse Events (AEs) and Serious Adverse Events (SAEs), as defined by the DHHP Office of Human Research Protections, will be monitored by the PIs [name]. AEs will be recorded by research staff on an AE form and discussed by the PIs during regularly scheduled meetings. The PIs will then prepare a written report for submission to the HFHS IRB and the appropriate NIH program officer. The report will include information regarding whether these events were expected or unexpected, the severity of the event, a brief narrative of the event, and a determination regarding any causal connection between the event and the ongoing research study. Any such events will also be included in the annual progress report send to NIH. In the unlikely event an SAE were to occur, research staff will alert the PI immediately. Subsequent reports to the HFHS IRB and NIH will be completed within 24 hours. The

expedited notice will be followed by a detailed report regarding the event as soon as possible.

All reports regarding events listed above will include study details (e.g. the title and grant number of the study and PI name), details of the event (date of occurrence, date that the MPIs became aware of these concerns), a detailed description of the event (including its impact on the participant), a detailed description of any steps taken to address the event, an attestation (including dates) that all required individuals/boards (including the HFHS IRB) have been notified, and any changes to the protocol or procedures that are proposed or implemented to prevent future occurrence of similar events.

This plan will also be reviewed by the Community Advisory Board, which will provide additional feedback to ensure the study team is addressing community-specific concerns regarding data and safety monitoring.

13.QUALIFICATIONS OF THE INVESTIGATOR(S)

[name] is an Associate Scientist at the Center for Healthy Policy & Health Services Research in Henry Ford Health Systems. She earned her PhD in child clinical psychology from Vanderbilt University with a minor specialization in quantitative methods. Her program of research centers on identifying risk factors for the onset of substance use in children and adolescents (e.g. [name] et al., 2015) as well as examining the role of early environmental and parenting factors associated with the trajectory of drug and alcohol use over time (e.g. [name] et al., 2020). She has specific expertise in assessment, research design, and data modeling techniques, having served as the PI, Co-I, or statistical consultant on a number of NIH-funded grants and published over 65 manuscripts and book chapters on the development of vulnerabilities to mental and behavioral health problems and targeted preventative interventions to reduce these risk factors.

14.REFERENCES

